## PREGNANCY

Women who enroll in the study shall be administered an over-the-counter pregnancy strip test to determine if the candidate is pregnant. The test strip to be used in the study is branded as the "Pregnancy hCG Test Strip", distributed by Pregmate located in Ft. Lauderdale, Florida. This product is demonstrated with a detection threshold of 25 IU/L and an accuracy level of 98%. This product features a control indicator to demonstrate validity of the test strip, and a results indicator – if the second indicator appears, this is a results of "pregnant". If the indicator does not appear, this is a results of "not-pregnant". Results of the test must be indicated on the

## **Inclusion/Exclusion with discussion of rationale; address both sexes and race allowance vs. availability**

Inclusion in the study consisted of the following criteria:

- Age equal to or above 18.
- Body Mass Index  $\geq 25$ .

Exclusion from the study consisted of the following criteria:

- Age equal to or below 17.
- Body Mass Index  $< 25$ .
- Open sores, wounds, or otherwise compromised skin in the treatment area
- History of keloid formation, hypertrophic scarring, or abnormal/delayed wound healing.
- Known or suspected pregnancy, or active nursing.
- General systemic conditions of arteriosclerosis or heart disease, anemia, aortic aneurysm, or hypertension.
- Liver conditions such as hyperlipidemia, hepatitis, liver disease, or abnormal liver function
- Diabetes or blood-glucose sensitivity
- Any prior invasive cosmetic surgery to the waist or abdominal area, such as liposuction.
- Hernias or diastasis recti within the treatment area.
- Concurrent, or within the last 6 months, participation in any clinical trial for another device or drug.
- Existing bacterial or viral infections (influenza, rhinovirus, hepatitis, pneumonia, tuberculosis, and the like)
- Presence of acne vulgaris, herpes zoster, psoriasis vulgaris, or similar skin conditions in the treatment area.
- Any type of cosmetic treatment to the target area within the last 6 months.
- Implanted active medical device anywhere in the subject, or metallic or polymeric implants in the vicinity of the treatment area.
- Currently undergoing, or recently underwent, chemotherapy or radiation treatment.
- Per the investigator's discretion, any physical or mental condition which may compromise the patient's safety or welfare.
- Failure to complete the study as outlined.

The primary rationale for the exclusion criteria that were identified is to ensure that any existing health conditions that may be adversely impacted by the use of this device are not aggravated or made worse. Additionally, exclusion of women who are pregnant or nursing is viewed as an appropriate precaution to prevent any possible complications to the fetus or nursing child that cannot presently be anticipated. For women who enroll for the study, a urine-based pregnancy test (Pregnancy hCG Test Strips, by Pregmate) shall be administered to determine if the subject is pregnant.

A secondary rationale for these exclusions is that the conditions and situations listed in the exclusions may contribute to a change in weight, skin condition, or the patient's response to the ultrasound energy which may obscure the resultant data and make it more difficult to objectively assess if the study objectives have been met. The exclusion of persons age 17 and under primarily is a matter of responsible consent and the prospective patient being capable of making an informed and rationale decision regarding the possible risks and benefits of the treatment, as well as being in a legally permissible status to elect a medical procedure on their own behalf.

The study will be conducted at a single existing medical clinic: Just the Right Curves, [name], with recruiting efforts being made in the immediate vicinity of this location.

During selection, the patient's gender, age, height, and ethnicity will be documented. The patient shall be provided with information regarding the treatment and the risks and benefits associated with the treatment, and provided with and asked to sign the informed consent. A copy of the informed consent is then provided to the patient.

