**Efficacy of Low-Frequency, High-Intensity Ultrasound  
for Reduction in Subdermal Adipose Layers**

Device Investigated: Ultimate Contour Body Sculpting Device

Indication Studied: Application of ultrasound for non-invasive waist circumference reduction.

A randomized, blinded comparison of waist circumference reduction of an active test group vs. a placebo control in adults.

Sponsor: CAO Group, Inc.

Protocol ID: 005-00036-8

Development Phase: Performance Validation

NCT ID: Not Yet Assigned

Anticipated Initiation Date: 15 December 2019

Anticipated Completion Date: 1 May 2020

Document Date: 10 October 2019

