#### **RECRUITMENT/SCREENING (total time of activity, 2-3 weeks):**

- Advertisement shall be made in social media channels regarding the study. This method is thought to be appropriate to bring the study to the attention to prospective participants located in the vicinity close to the study site.
- An appointment is made with a prospective patient, where the candidate is evaluated according to the inclusion and exclusion criteria, and medical history and medications. The purpose and protocol of this study are discussed, any candidate questions or concerns are addressed, and the consent form is presented. The candidate may sign the consent form at this time, or arrange for time to further review their participation. Women participating in the study who are of child-bearing age or capable of becoming pregnant shall take a pregnancy test. Patient Information, Medical History, and Medication forms are presented for the patient to populate.

- Recruitment continues until 50 included candidates are identified and consent obtained on those candidates.
- A candidate is accepted to participate after the following are confirmed by the principal investigator:
  - The Informed Consent Form is signed
  - The Patient Information Form is completed and the patient is not excluded due to any of the indicated criteria
  - The Medical History and Medication forms are populated and reviewed to ensure the candidate does not meet any of the exclusion criteria or other circumstances that may put the candidate at elevated risk by participating.

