**FOLLOW-UP (approximately 15 minutes):**

- The patient is scheduled for and arrives at the study site at the appropriate time points 1, 4, or 12 weeks after the final treatment.
- The date of the visit and the time of arrival will be documented Post-Assessment Measurement and Anticipated Effects forms.
- For the 1-week and 4-week visits, the patient fills out the WaistQ-Post Survey. For the 12-week follow-up, the WaistQ-12 Survey is filled out.
- The patient will have their waist circumference measured and documented by an investigator assigned to the post-treatment measurement and assessment activity, as described in the Measurement Tools and Methods section of this protocol. The patient will be asked for the study diary, and the investigator shall review the diary and discuss with the patient the items that are recorded about any abnormal body functions or observations that may be relevant to the treatment. If any are indicated, these will be documented in the patient record. The

investigator will also review observations and adverse events documented in previous sessions and discuss these with the patient. Additional record shall be made by the investigator as to whether past events and observations have been resolved or are still unresolved.

- For the 4-week or 12-week follow-up visits, the patient is provided with a study diary form, and instructed to document in the diary any unusual sensations, events, or bodily responses and to bring the form with them for the next visit. The patient is then scheduled for the 4-week or 12-week follow-up visits as appropriate.
- At the 12-week follow-up, additional review is made of the patient's Medical History and Medication forms and any new content for these forms is noted therein and discussed with the patient. If the 12-week follow-up visit is concluded and Adverse Event forms indicate any unresolved adverse results for the patient, additional follow-up is scheduled as appropriate until all adverse results are concluded.

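### Background weight loss is neither screened out at entry nor measured at follow-up, so it can add to the 1-inch waist result and, in a single arm, be credited to the device

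*Combined protocol and SAP*

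**What the plan says.** **Purpose of the exclusions.** Under *Inclusion/Exclusion with discussion of rationale*, safety comes first: "The primary rationale for the exclusion criteria that were identified is to ensure that any existing health conditions that may be adversely impacted". Data quality comes second: "the conditions and situations listed in the exclusions may contribute to a change in weight". That sentence goes on to name skin condition and response to ultrasound as further things the exclusions protect.

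**What the list covers.** The Synopsis and the Investigational Plan each carry a list. Both bar "Any type of cosmetic treatment to the target area within the last 6 months". Neither names a current weight-loss diet, programme or medication, a recent weight change, or a need for stable weight. The nearest general criterion is discretionary and tied to safety: "any physical or mental condition which may compromise the patient's safety or welfare".

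**Use of the forms.** At screening the Medical History and Medication forms are "reviewed to ensure the candidate does not meet any of the exclusion criteria or other circumstances that may put the candidate at elevated risk". At week 12, "additional review is made of the patient's Medical History and Medication forms and any new content for these forms is noted therein"; the investigator then talks the new entries over with the patient. No analysis depends on what is found.

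**Measurements.** The Synopsis (*Methodology*) has patients weighed before each treatment. *FOLLOW-UP* lists waist circumference, surveys, diary and adverse-event review, but not weight. *RECRUITMENT/SCREENING* lists no waist reading, so baseline is the value taken just before treatment 1.

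**Success.** *Methodology* and *Study Objectives* require a waist reduction of at least 1 inch from baseline to 12 weeks after the last treatment. *Study Objectives* adds statistical significance.

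**Design.** *Study configuration* describes a single arm. The title page describes a randomized placebo comparison, the Synopsis *Statistical Methods* compares test with control, *Study Objectives* mentions a Test group, and *Sequence and duration of study period* mentions assignment to a study group.

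**The concern.** *Study Objectives* attributes the change in waist from baseline to week 12 to the ultrasound. A volunteer with a BMI of 25 or more who is already dieting or taking a weight-loss drug, and is otherwise healthy, meets no listed exclusion. Any waist loss from that source enters the primary endpoint in the direction of success.

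The sponsor evidently sees the problem. It cites weight change as a reason for its exclusions, and its *Introduction* faults earlier studies for not accounting for healthy-lifestyle instructions. The list does not carry that intention through. Because weight is not listed after the last treatment, a reader of the results could not tell how much of the waist change came with general weight loss over the final 12 weeks. Eligibility and unrecorded weights cannot be repaired after enrolment.

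**Working it through.** **Inputs from the protocol.** Sessions 6 to 8 days apart, three sessions, endpoint 12 weeks after the last (*Methodology*). SD 1.50 inches, target 1.0 inch, a cited typical response of 0.75 inch, minimum of 40 patients (*Sample size*).

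**Assumptions.** The 1-inch criterion applies to the group mean (the protocol does not say whether it means the mean or each patient). Changes are normal with SD 1.5. Drift adds to any device effect. The amount of drift is not in the documents and is varied from 0 to 1.0 inch.

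**1. The plan's own figure.** n = 2 × (1.96 + 0.84)² × 1.5² / 1.0² = 35.28, rounded up to 36. A two-sample t calculation gives 36.3, rounded up to 37, which matches the stated 37. The inputs can be used as they stand.

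**2. Exposure window.** Two gaps of 6 to 8 days are 12 to 16 days; adding 84 days gives 96 to 100 days from baseline to endpoint.

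**3. How drift might arise (illustrative).** If a fraction p of patients lose L inches by their own efforts, the mean shifts by p × L. For p of 10%, 25% or 50% and L of 1 or 2 inches, this runs from 0.10 × 1 = 0.10 inch to 0.50 × 2 = 1.0 inch. A quarter of patients losing 1 inch gives 0.25 inch.

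**4. Single arm, no device effect, n = 40.** The standard error is 1.5/√40 = 0.237 inch. The chance of an observed mean of at least 1 inch is Φ((drift − 1)/0.237). The chance of a significant fall from zero is Φ(drift/0.237 − 1.96). The share of patients losing at least 1 inch is Φ((drift − 1)/1.5).

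| Drift (inch) | Mean ≥ 1 inch | Significant fall from zero | Patients losing ≥ 1 inch |
|---|---|---|---|
| 0.25 | 0.08% | 18% | 31% |
| 0.50 | 1.8% | 56% | 37% |
| 0.75 | 15% | 89% | 43% |
| 1.00 | 50% | 99% | 50% |

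Significance alone needs an observed mean of only 1.96 × 0.237 = 0.465 inch. The comparison with zero is itself an assumption, since *Statistical methods planned* names no comparator for the ANOVA.

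**5. Drift added to a partial device effect.** If the device gives 0.75 inch and there is no drift, the chance of a mean of at least 1 inch is Φ((0.75 − 1)/0.237) = Φ(−1.054) = 15%. With 0.25 inch of drift the expected mean is 1.0 inch and the chance is 50%. The 50% does not depend on the SD or the sample size. The 15% does: it is 16% at n = 37 and 12% at n = 50 with SD 1.5, and 6% at n = 40 with SD 1.0.

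**6. Two arms.** Let both arms share an expected drift δ and let the device effect be τ. The between-group contrast has expectation (τ + δ) − δ = τ, so δ drops out. The treated arm's own change has expectation τ + δ, so the absolute 1-inch criterion still includes δ.

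**The case against.** **Drift alone is unlikely to meet the criterion.** This stands. It would have to average about 1 inch for an even chance, and at 0.5 inch the chance is about 2%.

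**A seasonal reading is tempting but unsupported.** The title page gives "Anticipated Initiation Date: 15 December 2019" and a completion date of 1 May 2020. With 96 to 100 days per patient, baselines would fall from mid-December to late January and endpoints from late March to 1 May. A reader might infer that ordinary winter-to-spring waist loss could meet the goal. The documents give neither a size nor a direction for seasonal change, the dates are only anticipated, and replacement enrolment would fall later. The point does not rest on season.

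**The exclusions do not promise to remove every cause of weight change.** Also fair. The rationale describes the conditions that are listed, is expressly secondary, and covers skin condition and response to ultrasound as well, so the skin and cosmetic-treatment criteria are not misplaced. What remains is that an obvious cause of the outcome is missing from a list partly meant to protect it.

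**Weight is not ignored.** It is taken before treatments, is named as an efficacy input, and would enter the planned correlation analysis. None of this reaches the 12 weeks after the last treatment.

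**The Medication form might catch a weight-loss drug.** The elevated-risk check could, at discretion, but it addresses safety. Restrictions on patients may also appear in consent pages or an operator's manual that were not available, so their absence cannot be fully confirmed.

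**A control group would solve most of this.** True for the between-group test, and the design conflict is the larger issue. It does not protect the absolute 1-inch criterion.

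**Conclusion.** The point holds as a gap in eligibility and measurement. Background weight loss is not excluded at entry and weight is not listed at the endpoint visit, so it adds to the 1-inch result. The consequence is greatest if *Study configuration* governs, because a single arm cannot separate drift from device effect. It is narrower, but not absent, under the randomized placebo wording.

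The realistic danger is drift that tops up a partial effect: 0.25 inch moves the chance of success from about 15% to 50% if the device delivers the cited 0.75 inch. Drift can also produce a significant fall from zero without any device effect (56% at 0.5 inch), although significance alone does not satisfy the primary objective. These figures assume n = 40, SD 1.5, a group-mean criterion and drift values that the documents do not supply. They show sensitivity and are not an estimate of the bias that will occur. This is a worthwhile, low-cost improvement; it does not replace a control group.

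**What to change.** 1. **Eligibility.** Add to both copies of the list an exclusion for a current weight-loss diet, programme or medication, and for self-reported weight change above a stated limit in the previous 3 months. Cost: some screen failures and slower recruitment.
2. **Weight at follow-up.** Record weight at the 1-, 4- and 12-week visits and report waist change alongside weight change as a supportive analysis. Cost: a brief measurement at visits already planned.
3. **Measures started after baseline.** Record any weight-loss measure or other abdominal cosmetic treatment started before week 12. Repeat the primary analysis without those patients as a sensitivity analysis only, and state that this selects on post-baseline behaviour.
4. **Optional screening waist.** Take one tape reading at the existing screening appointment and report the change to treatment 1 descriptively. That interval is undefined in length and cannot estimate drift over about 14 weeks.
5. **Reconcile the text.** The title page, Synopsis *Statistical Methods*, *Study Objectives*, *Study configuration* and *Sequence and duration of study period* must agree on the design. Any condition on lifestyle change must be reconciled with the planned lifestyle advice. *Methodology* places that advice after the final treatment, inside the endpoint window, while *Device description and settings* places it at the conclusion of the study; those two sections must also agree.

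Items 1 to 4 add no visits.

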### **Details of the treatment protocol**

#### **STUDY STAFF**

- Principal Investigator - Licensed medical doctor. Discuss patient adverse interactions, and directly observe patient adverse interactions following treatment; Supervise overall execution of the study protocol, including study documentation;
- Treatment Clinician - Directly trained by sponsor in the use and application of the device. Licensed medical doctor. Responsible for application of the device to the patient. This staff shall not be permitted to serve as Assessment staff.
- Assessment Clinician - Directly trained by sponsor in the use and application of the measurement tool to be used for this study. Licensed medical doctor. Responsible for measuring the patient's waist circumference and documenting such in the patient record. This staff shall not be permitted to serve as Treatment staff.
- Clerical Staff - Directly trained by the sponsor on the study protocol and the use and management of forms associated with this study. Minimum of a high school diploma. Responsible for receiving patients at arrival and scheduling next visits, and for providing and collecting study records from each of the clinicians. May also assist with organization of study records.

#### **RECRUITMENT/SCREENING (total time of activity, 2-3 weeks):**

- Advertisement shall be made in social media channels regarding the study. This method is thought to be appropriate to bring the study to the attention to prospective participants located in the vicinity close to the study site.
- An appointment is made with a prospective patient, where the candidate is evaluated according to the inclusion and exclusion criteria, and medical history and medications. The purpose and protocol of this study are discussed, any candidate questions or concerns are addressed, and the consent form is presented. The candidate may sign the consent form at this time, or arrange for time to further review their participation. Women participating in the study who are of child-bearing age or capable of becoming pregnant shall take a pregnancy test. Patient Information, Medical History, and Medication forms are presented for the patient to populate.

- Recruitment continues until 50 included candidates are identified and consent obtained on those candidates.
- A candidate is accepted to participate after the following are confirmed by the principal investigator:
  - The Informed Consent Form is signed
  - The Patient Information Form is completed and the patient is not excluded due to any of the indicated criteria
  - The Medical History and Medication forms are populated and reviewed to ensure the candidate does not meet any of the exclusion criteria or other circumstances that may put the candidate at elevated risk by participating.

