### **Methodology**

Samples of the test device (Ultimate Contour Mini by CAO Group, West Jordan, Utah, U.S.A.) will be provided for the test. The devices consist of a touch screen interface whereby the operator may select the intensity of the delivered energy and the duration of treatment. The device features a single output cable to which is attached the ultrasound handpiece assembly. For the purposes of this test, the duration of treatment will be set at 30 minutes, and the intensity set at Level 4 (the maximum the device is capable of).

Application of the ultrasound energy consists of applying a treatment gel or liquid to the patient's skin (to eliminate air gaps between the applicator and the skin) and gently kneading the skin in circular motions, slowly progressing across the surface of the treatment area, making methodical passes until the entire treatment area has been exposed, then returning to the origin point and repeating this application approach.

Following treatment, the patient will be asked regarding the extent of discomfort experienced during the ultrasound application, and assessment will be made by a blinded, independent evaluator whether a number of visible skin conditions are observed or experienced by the patient.

Prior to the first treatment, the patient's weight and height will be measured by the blinded, independent evaluator, and the patient's waist circumference measured using a constant-tension flexible tape measure. Each patient will be treated a total of three (3) times, with a gap of 6-8 days between each treatment. Prior to each treatment, the patient will be weighed. Following the final treatment, the patient will be advised of support mechanisms (healthy diet, exercise, and so forth) to support a successful outcome. At 1, 4, and 12 weeks after the last treatment, the patient will be recalled for a final measurement and review of any outstanding adverse events. Study success shall be determined by achieving at least 1 inch of waist reduction between the initial measurement and the 12-week follow-up.

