#### TREATMENT (total time of activity, 14-18 weeks - 4-6 weeks for the 1st, 2nd, and 3rd treatment applications, and 12-14 weeks following the 3rd treatment for follow-up visit):

##### Individual Treatment Session (approximately 70 minutes)

###### Prior to the Treatment (about 10 minutes):

- The patient is scheduled to arrive at the study site to undergo a treatment.
- The date of the treatment and the time of arrival will be documented in the treatment session record.
- During the first treatment only: The patient is given the Q-Pre Survey to fill out.
- The assigned pre-treatment investigator measures the waist circumference of the patient and documents this in the Pre-Treatment record, with these measurements being made by the blinded assessment clinician as described in the Measurement Tools and Methods section of this protocol.
- Prior to Treatments 2 and 3, the patient will be asked for the study diary, and the pre-treatment investigator shall review the diary and the patient's previous post-treatment Anticipated Effects and Adverse Event forms and discusses with the patient the items that are recorded about any abnormal body functions or observations that may be relevant to the treatment. If any are indicated, these will be documented in the patient record. Additional record shall be made by the investigator as to whether past events and observations have been resolved or are still unresolved.
- The patient is moved to the treatment area.

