###### Application of the Treatment (approximately 45 minutes):

- The treatment clinician prepares the patient for treatment by displacing clothing from the treatment area, which is the abdominal area from the bottom of the sternum to the iliac crest.
- The patient lies down on their back on the treatment table.
- The treatment clinician turns on the Ultimate Contour Mini device and sets it to the indicated parameters for this study: Time Setting of 30 minutes; Intensity Setting of 4.
- The treatment oil/fluid, a massage oil with a cottonseed or grapeseed oil base, is applied to the patient's skin over the area intended for exposure.

- The treatment clinician applies the treatment handpiece to the patient's skin in the intended treatment area.
- The treatment clinician presses the Activation button on the Ultimate Contour screen to begin energy emissions from the handpiece.
- The treatment clinician begins moving the handpiece along the skin with slight pressure to the handpiece to maintain contact with the skin, moving in circular, orbital motions approximately twice the diameter of the handpiece diameter, and progressively advancing in a linear direction from one edge of the treatment zone to the other in an overall back-and-forth approach.
- The treatment clinician continues application of the handpiece until either the proscribed 30 minutes has expired, or the patient indicates to halt the treatment due to discomfort.
- Once energy emissions cease, the handpiece is removed from the skin, and the treatment oil is cleaned off from the skin.
- The patient replaces clothing and is moved back to the assessment room.

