#### **SAFETY**

Input variables related to safety are reflected in the exclusion criteria. Primary among these is the effect the ultrasound treatment has on existing illnesses or conditions. There is concern that the delivered energy could adversely affect these conditions, making the patient's overall status worse. Other input variables for safety include the effect on localized tissue directly exposed to the ultrasound, as well as possible systemic effects that may occur.

Output data collected for safety include the patient's assessment of pain or discomfort experienced during or following the treatment, and questioning regarding any observations about systemic health that the patient may make during the overall trial. Any such comments or concerns from the patient are documented in the patient treatment records. Additionally, observations by the clinician about localized tissue response and patient general behavior were collected if any occurred and made part of the patient record.

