#### **ADVERSE INTERACTIONS**

Anticipated adverse responses include:

- Localized inflammation, edema, and elevated temperature of the treatment area: Based on the proposed mechanism of action, the application of ultrasound and the disruption of cells could result in a localized increase in tissue temperature, accompanied by increased blood circulation through the insulted tissue.
- Localized pain or discomfort: The action of ultrasound of this frequency and intensity on nerve cells is not well understood. The same mechanism of action could trigger nervous cell responses interpreted by the brain as a pain response. The disruption and cavitation of adjacent adipose cells could also trigger a pain response.
- Possible system disruption: The applied ultrasound energy is intended to provide localized energy at the typical depth of tissue where sub-dermal adipose cells are found. The ultrasound energy could continue to propagate further into the body, reaching gastro-intestinal organs beneath the treated area. In generalized terms, there could be disruptions to digestive processes resulting from exposure to the ultrasound energy.

- Possible elevation of blood glucose levels: The disruption and lysis of adipose cells may release an increased amount of glycogen into the blood stream. Patients who present with diabetes or pre-diabetes or who are susceptible to variations in blood glucose levels may experience side-effects consistent with elevated glucose levels wherein they are unable to metabolize and/or process the glucose products adequately.
- Possible pigmentation changes of the skin: The action of ultrasound on the skin may alter the amount or chemical nature of pigments in the skin, causing discolorations relative to the surrounding skin.
- Possible aggravation of surgically compromised or wounded tissue: The action of ultrasound on tissue that has been disrupted, such as through surgical procedures, previous wounds, or previously or presently inflamed tissue, could create mechanical stresses on the wound boundaries and possible overcome connective tissues across the wound boundaries, resulting in re-opened or inflamed sites.

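### No pregnancy check is listed after the recruitment appointment, so no listed step is designed to detect a pregnancy that begins before the last treatment (low severity, cheap to fix)

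*Combined protocol and SAP*

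**What the plan says.** Known or suspected pregnancy is an exclusion in both the synopsis and the body of the protocol. The rationale section explains that "exclusion of women who are pregnant or nursing is viewed as an appropriate precaution to prevent any possible complications to the fetus".

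The Recruitment/Screening section places the test at the recruitment appointment: "Women participating in the study who are of child-bearing age or capable of becoming pregnant shall take a pregnancy test". The Pregnancy section and the rationale section also require a urine strip for women who enroll, without a time or a repeat.

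The steps under Prior to the Treatment are the arrival record, the Q-Pre Survey (first session only), the waist measurement and one further review: "Prior to Treatments 2 and 3, the patient will be asked for the study diary". In that review the investigator discusses the diary and the earlier effect and adverse-event forms with the patient. Application of the Treatment and Post-Treatment Assessment add no pregnancy check.

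The next formal review of history and medication is in Follow-up: "At the 12-week follow-up, additional review is made of the patient's Medical History and Medication forms". All three treatments are over by then.

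Other steps touch on eligibility. The synopsis says "Prior to each treatment, the patient will be weighed", and the Safety section collects "questioning regarding any observations about systemic health that the patient may make during the overall trial".

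**The concern.** The sponsor chose to keep pregnant women away from this exposure, but the listed procedure checks for pregnancy once, before a series of treatments that ends at least 12 days later. A woman who conceives in between and does not suspect it could go through all the listed steps and be treated for 30 minutes at the device's maximum intensity. The treatment area is "the abdominal area from the bottom of the sternum to the iliac crest".

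The plan's own list of anticipated adverse responses gives a reason for caution: "The ultrasound energy could continue to propagate further into the body, reaching gastro-intestinal organs beneath the treated area". The stake is patient safety. No endpoint definition, analysis or sample size depends on it.

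**Working it through.** The plan states no figure on this point, so there is none to reproduce. The check is a comparison of sections followed by simple arithmetic.

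**1. What each later step can detect**
- Weighing before each treatment bears on BMI, and sight of the bare abdomen bears on skin conditions. Neither is aimed at pregnancy.
- Questioning on systemic health depends on what the patient notices.
- The diary is first handed out after session 1. Its review before sessions 2 and 3 might bring up a missed period by chance, but it cannot help at session 1.
- The week-12 review comes after all exposure.

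**2. Interval from the test to treatment**

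Inputs from the plan: recruitment 2 to 3 weeks; treatment phase 4 to 6 weeks; three sessions 6 to 8 days apart.
- Minimum to session 3, with screening and session 1 on the same day: 2 × 6 = 12 days.
- Overlapping phases, session 1 falling 0 to 7 days after screening (assumption): 12 to 7 + 16 = 23 days. Mean to session 1 is 3.5 days = 0.5 week; mean to session 3 is 3.5 + 14 = 17.5 days = 2.5 weeks.
- Sequential phases (assumption): with R weeks of recruitment and T weeks of treatment, and uniform spread within each, the mean to session 1 is R/2 + (T − 2)/2. R = 2, T = 4 gives 2.0 weeks; R = 3, T = 6 gives 3.5 weeks. Two weeks more to session 3 gives 4.0 and 5.5 weeks.
- Sequential maximum: 3 + 6 = 9 weeks = 63 days to session 3, and 63 − 12 = 51 days to session 1.

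The plan does not say that the phases run in sequence. Two provisions point that way: training runs alongside recruitment, and the sponsor obtains signed consent copies before it delivers devices.

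**3. Expected conceptions**

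The plan recruits 50 patients with the sexes roughly balanced, so about 25 women. Assumptions: 10 to 25 of them can conceive, at 1% to 10% per woman-year. Expected number = women × yearly rate × weeks / 52.

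| Conceptions after screening and before | Low | High |
|---|---|---|
| Session 3 | 10 × 0.01 × 2.5/52 = 0.005 | 25 × 0.10 × 5.5/52 = 0.26 |
| Session 1 | 10 × 0.01 × 0.5/52 = 0.001 | 25 × 0.10 × 3.5/52 = 0.17 |

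The second row is the relevant one for a strip on the day of session 1. It is an upper limit for conceptions that began after screening, because a urine strip misses very recent ones.

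**4. Wrong strip results**

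The Pregnancy section states 98% accuracy, read here as 2% wrong results per strip.
- 10 strips: 10 × 0.02 = 0.2 wrong. 25 strips: 25 × 0.02 = 0.5 wrong.
- Chance of at least one wrong in 25: 1 − 0.98^25 = 0.40.
- Two wrong in a row, if errors are independent: 25 × 0.02² = 0.01.
- Wrong results per conception found: about 0.5/0.17 = 3 to 0.2/0.001 = 200.

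**The case against.** The strongest objection is that absence from the visible procedure is not absence from the trial. The Pregnancy section breaks off in the sentence on where the result is recorded. The Q-Pre Survey (completed before session 1), the record forms, the consent pages and the operator's manual, which covers the conversations with patients, are not available. Any of them could ask about pregnancy or tell the patient to report it. This stands, and it limits the point to the listed steps.

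A second objection is yield. A session 1 strip would produce more wrong results than true findings. If the phases overlap, session 1 is at most 7 days after screening and nearly every new conception would be too recent to show. This also stands. It is why the severity is low and why a repeat strip is part of the fix.

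Third, the hazard is inferred. The plan names gastro-intestinal organs and documents no specific fetal harm. That is correct, but the sponsor has already judged exclusion an appropriate precaution, and the point asks only that the precaution remain in force while treatment continues.

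Three stronger readings are tempting, and the documents do not support them:
- A reader might infer that a new pregnancy would certainly go undetected. The diary discussion before sessions 2 and 3 and the unseen forms rule out so firm a statement.
- A reader might take 0.005 to 0.26 as the number of exposures that a session 1 strip would prevent. That range runs to the last treatment, and the strip cannot reach conceptions after session 1.
- The rationale section says that excluded conditions may obscure the data, so a reader might infer a threat to the waist result. At well under one expected case, none is shown.

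**Conclusion.** The point holds as a low-severity patient-safety improvement. On the visible text, the only timed pregnancy test is at recruitment and no listed step is designed to detect a pregnancy that begins before the last treatment. The 12-day minimum follows from the plan's own visit spacing. The 9-week maximum rests on strictly sequential phases. The conception counts rest on assumed numbers of women able to conceive, assumed yearly rates and assumed lags, none of which the plan gives. Across those ranges the expected number of affected women is well below one. The case for acting is therefore that the check is cheap and serves a precaution the sponsor has already adopted, not that the event is likely.

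**What to change.** Add to Prior to the Treatment:
- For women capable of becoming pregnant, repeat the already specified urine hCG strip on the day of session 1, before treatment.
- At every session, record any new history or medication and, for women capable of becoming pregnant, the date of the last menstrual period and whether pregnancy is possible.
- Repeat the strip before session 2 or 3 if a period is late or pregnancy is possible.
- Withhold treatment on a positive strip until a repeat strip and the investigator resolve it.

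The date of the last period is included because a question about suspected pregnancy alone is weak when the pregnancy is unsuspected.

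Cost, at an assumed 1 to 2 minutes per set of questions and 5 minutes per strip:
- Questions: 50 × 3 = 150 sessions, 2.5 to 5 hours in total.
- Session 1 strips: 10 to 25, or 0.8 to 2.1 hours.
- Upper limit, if all 25 women are tested at all three sessions: 75 strips, 6.25 hours, with 75 × 0.02 = 1.5 wrong results expected and a 1 − 0.98^75 = 0.78 chance of at least one.

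No new staff or test product is needed. The downside is an occasional false positive that briefly delays treatment. The change narrows the gap but does not close it, because a strip still misses very recent conceptions.
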